### **2.4.2 Prior and concomitant therapies**

Prior / concomitant medications / non-drug therapies will be collected in the corresponding CRF and will be coded using the WHO dictionary and the MedDRA dictionary accordingly. The medications / non-drug therapies will be classified into prior, core part concomitant, and extension part concomitant.

- The prior (pre-baseline) medications / non-drug therapies will be defined as medications / non-drug therapies with the end date prior to the first dose date of study treatment.
- The core part concomitant medications / non-drug therapies will be defined as medications / non-drug therapies with the end date on or after the first dose date of study treatment (or no documented end date) and the start date on or prior to the switching date.
- The extension part concomitant medications / non-drug therapies will be defined as medications / non-drug therapies with the end date after the switching date (or no documented end date).

The prior medications will be summarized by treatment group, anatomical therapeutic chemical (ATC) class and PT for core part analyses only. The concomitant medications will be summarized by study part, treatment group, ATC class and PT. For the extension part, the summary will be provided using OLS.

The prior non-drug therapies will be summarized by treatment group, SOC and PT for core part analyses only. The concomitant non-drug therapies will be summarized by study part, treatment group, SOC and PT. For the extension part, the summary will be provided using OLS.

The following lipid-lowering therapies will be identified from the medications, using the ATC class and the PT. Detailed specifications will be provided separately.

- Statins
- Cholesterol absorption inhibitor
- PCSK9 inhibitor monoclonal antibody
- Inclisiran
- Other lipid lowering therapy

Any above lipid-lowering therapy added after study Day 1 will be summarized by treatment group and medication, using the numbers and the percentages of participants who received the corresponding medication on or prior to the following select time points.

- Study day 1
- Study day 90
- Study day 150
- Study day 180
- Study day 270
- Study day 330
- Study day 360

In core part analyses, the above new added LLT summary table will include time points up to study Day 180 only. In final analyses, summary table of new added LLT will be provided including the time points from study Day 180 up to study Day 360 using OLS.

## **2.5 Analysis supporting primary objective(s)**

The FAS will be used for the primary efficacy analysis.

### 2.5.1 Primary endpoint(s)

The primary objective of this study is to demonstrate the superiority of inclisiran as monotherapy, compared to placebo, on mean percentage change from baseline in LDL-C at Day 150, in Chinese adults with low or moderate ASCVD risk and elevated LDL-C who are not on any lipid lowering therapy.

The primary endpoint is the percentage change from baseline at Day 150 in LDL-C.

### 2.5.2 Statistical hypothesis, model, and method of analysis

The primary efficacy endpoint will be analyzed using an Analysis of Covariance (ANCOVA) model, in which the response variable will be the percentage change from baseline at Day 150 in LDL-C, treatment will be included as fixed-effect factor and baseline LDL-C will be included as a covariate.

The primary statistical hypothesis is stated as below.

- $H_0$ : the mean difference (inclisiran minus placebo) in percentage change from baseline at Day 150 in LDL-C is no less than zero.
- $H_1$ : the mean difference (inclisiran minus placebo) in percentage change from baseline at Day 150 in LDL-C is less than zero.

The study can be claimed a success if the null hypothesis ( $H_0$ ) is rejected at the one-sided significance level of 0.025.

The statistical test will be performed at the one-sided significance level of 0.025 based on the ANCOVA model. The estimate and the 95% confidence interval will be provided for the adjusted mean difference between inclisiran and placebo, and for the adjusted mean for both inclisiran and control groups, based on the ANCOVA model. The one-sided p-value will be provided for the primary null hypothesis.

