⁹ Required for any female participant who is considered as surgically sterile or post-menopausal in the absence of medical documentation confirming this reproductive/menopausal status at screening.

¹⁰ Performed by the central lab. Fasting lipid profile includes LDL-C, total cholesterol, triglycerides, HDL-C, non-HDL-C, ApoA1 and Apo B. The fasting lipid profile results will not be reported to the site except the screening visit, and will be blinded for participants, investigators, site staff, persons performing the assessments, monitors and the Novartis Clinical Trial Team (CTT) until the core part database lock. After the core part database has been locked, fasting lipid profile results should remain blind to the participants, investigators and site staff throughout the study until final database lock.

¹¹ Performed by the central lab. The results will not be reported to the site and will be blinded for participants, investigators, site staff, persons performing the assessments, monitors and the Novartis Clinical Trial Team (CTT) until the core part database lock. After the core part database has been locked, Lp(a) and PCSK9 results should remain blind to the participants, investigators and site staff throughout the study until final database lock.

¹² Subcutaneous inclisiran/placebo will be administered by qualified personnel after all other study assessments have been completed for this visit

2 Introduction

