#### **Baseline assessment**

For each variable, the baseline assessment is defined as the last non-missing assessment (scheduled or unscheduled) collected on or prior to the first dose of study treatment, unless otherwise specified. If a participant has never started any study treatment, then the last non-missing assessment (scheduled or unscheduled) collected on or prior to the study Day 1 will be used as baseline assessment.

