### **2.6.1 Secondary endpoint(s).**

#### **2.6.1.1 Secondary efficacy endpoints for core part**

The secondary efficacy endpoints for core part are listed as follows:

- Absolute change in LDL-C from baseline at Day 150
- Percentage and absolute change in PCSK9, TC, HDL-C, non-HDL-C, ApoB, ApoA-1, Lp(a) and TG from baseline at Day 150

All secondary efficacy endpoints for core part will be analyzed using the same ANCOVA model as for the primary efficacy endpoint. Lp(a) will be log-transformed before modeling. The model will include treatment as fixed effect, and baseline value as a covariate. The adjusted mean difference between inclisiran and placebo and corresponding two-sided 95% CIs will be provided separately. Nominal two-sided p-values will also be provided.

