## **3 Sample size calculation**

This study is designed to randomize approximately 200 Participants (with randomization ratio of 1:1 to inclisiran and placebo arms) in order to provide adequate information to characterize the safety profile of inclisiran as well as to have sufficient power for the primary efficacy endpoint.

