### 5.3 Laboratory parameters derivations

For laboratory measurements below the lower limit of quantification (LLQ), LLQ/2 will be used as the numeric value for the measurement. For example, if numeric result is missing in the database and character result is “< 3”, the numeric result should be treated as 3/2 = 1.5 during analysis

For fasting glucose, only measurements taken in a fasting state will be used. Baseline glucose is defined as the average of the last two non-missing fasting glucose values on or prior to Day 1. If only one non-missing fasting glucose value is available on or prior to Day 1, the available value will be used as baseline.

Notable laboratory values are defined in [Table 5-1](#):

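### The Day 150 ANCOVAs are valid but adjust for one pre-dose lipid value only, leaving some precision from the screening lipid profile unused

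*SAP*

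**What the plan says.** **Model.** For the primary endpoint, "treatment will be included as fixed-effect factor and baseline LDL-C will be included as a covariate" (SAP 2.5.2; Protocol 9.3.2 agrees). For the secondary Day 150 endpoints, "The model will include treatment as fixed effect, and baseline value as a covariate" (SAP 2.6.1.1; Protocol 9.4.1.1 agrees).

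**Baseline.** SAP 2.1.1 defines it as "the last non-missing assessment (scheduled or unscheduled) collected on or prior to the first dose of study treatment", so it is a single value. The imputation models in SAP 5.4.1.1 also carry one pre-dose value.

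**Screening sample.** Footnote 10 to Protocol Table 1-2 describes a central-laboratory fasting profile of LDL-C, total cholesterol (TC), triglycerides (TG), HDL-C, non-HDL-C, ApoA-1 and ApoB. It adds: "The fasting lipid profile results will not be reported to the site except the screening visit". A profile is therefore taken at screening. Protocol 1.3 requires a fast of at least 10 hours for every visit, and Protocol 4.1 limits screening to 14 days. Screening LDL-C decides eligibility (130 to below 190 mg/dL, Protocol 5.1). The text does not settle whether PCSK9 and Lp(a) are measured at screening.

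No sensitivity or supplementary analysis (SAP 2.5.5, 2.5.6) adds the screening value, and neither document says why it is left out.

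**The concern.** A single lipid reading is noisy. Noise in the Day 1 value enters the analysis twice, as the denominator of the percentage change and as the covariate. A second reading of the same analyte, taken days earlier by the same laboratory under the same fasting rule, carries independent information about the participant's underlying level. It precedes randomisation, so adjusting for it brings no bias and leaves the estimand unchanged.

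What is at stake is interval width, mainly for the secondary endpoints. The stated objective for TG, HDL-C, ApoA-1 and the others is to demonstrate efficacy, yet Protocol 9.9.2 assesses no power for them and the effects on some may be small.

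**Working it through.** **1. The plan's own figure.** SAP section 3 says: "This study is designed to randomize approximately 200 Participants (with randomization ratio of 1:1 to inclisiran and placebo arms", in order "to have sufficient power for the primary efficacy endpoint". It gives no effect size, SD, power or dropout, so 200 cannot be reproduced. A range check stands in for it:
- Inputs from the documents: 100 per arm, and a null hypothesis that "is rejected at the one-sided significance level of 0.025". The differences run from 30 points (Protocol 4.2 mentions 30–40% as a sufficient reduction) to 57.2 points (the Asian phase 3 result in Protocol 2.2).
- Assumed: SD 15 to 40 points.
- Worst case, difference 30 and SD 40: SE = 40 × √(2/100) = 5.66; 30/5.66 = 5.30; 5.30 − 1.96 = 3.34; power = Φ(3.34) = 0.9996.
- Per arm for 90% power in that case: 2 × (1.96 + 1.282)² × (40/30)² = 37.4, so 38.

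The primary test has ample power with or without a second covariate.

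**2. Idealised ceiling.** Suppose the screening, Day 1 and Day 150 values are equally correlated at r, with no eligibility cut and no variation in drug response. Residual variance is 1 − r² with one pre-dose value and (1 − r)(1 + 2r)/(1 + r) with two. The ratio is (1 + 2r)/(1 + r)².

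| r | Variance ratio | SE reduction |
|---|---|---|
| 0.3 | 1.6/1.69 = 0.947 | 2.7% |
| 0.5 | 2.0/2.25 = 0.889 | 5.7% |
| 0.7 | 2.4/2.89 = 0.830 | 8.9% |
| 0.8 | 2.6/3.24 = 0.802 | 10.4% |

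**3. LDL-C under this trial's conditions.** Percentage change was simulated with screening LDL-C cut at 130 to below 190 mg/dL, and ANCOVA on Day 1 alone was compared with ANCOVA on Day 1 plus screening. Assumed: between-person CV 15–25%, within-person CV 6–12%, mean reduction 50% with response SD 10 or 20 points, and extra drift to Day 150 of 0 or 10%. SE = residual SD × √(2/100); half-width = 1.96 × SE.

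| Between / within CV, response SD, drift | Residual SD | Variance ratio | SE | 95% CI half-width |
|---|---|---|---|---|
| 25% / 6%, 10, none | 9.59 → 9.27 | 0.934 | 1.356 → 1.311 | 2.66 → 2.57 |
| 20% / 9%, 10, none | 11.79 → 11.44 | 0.941 | 1.667 → 1.618 | 3.27 → 3.17 |
| 20% / 9%, 20, none | 17.00 → 16.76 | 0.972 | 2.404 → 2.370 | 4.71 → 4.65 |
| 15% / 12%, 20, 10% | 20.61 → 20.44 | 0.983 | 2.915 → 2.890 | 5.71 → 5.67 |

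The first and last rows are the extremes of the grid: variance falls by 1.7% to 6.6%, and SE by 1% (√0.983 = 0.991) to 3% (√0.934 = 0.966). With within-person CV held to 6–10%, the fall was 2–6%, which I take as the working range. In every scenario the estimated difference was the same under both models. The gain is below the ceiling because eligibility narrows the range of the screening value and because that value does not predict variation in drug response.

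**4. TG and HDL-C.** Assumed within-person CV: 20–30% for TG, 6–8% for HDL-C.
- HDL-C, no drift: SE 1.32 → 1.19 and 1.68 → 1.52, so variance falls by 1 − (1.19/1.32)² = 18.7% and 1 − (1.52/1.68)² = 18.1%.
- HDL-C with drift (between-person CV 22%): 7–14% when the true drift or response SD is 8–12 points, and 5–8% at 15 points.
- TG, no drift: about 8–13%.
- TG with drift or response SD of 20–30 points (between-person CV 35%): 4.5–8%.

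Rounded over the runs: HDL-C about 5–20%, TG about 5–13%. TC, non-HDL-C, ApoB and ApoA-1 were not simulated.

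**5. Timing.** The SAP history labels Amendment 1 (22 April 2024) as before core part lock and Amendment 2 (21 August 2024) as before final lock. The core part may therefore already have been locked by Amendment 2; the documents do not say outright.

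**The case against.** - **It is a preference.** ANCOVA on treatment and baseline is valid, pre-specified, and the same in protocol and SAP. This stands. A reader might infer that the primary analysis is biased or underpowered; nothing in the documents supports that.
- **It changes nothing for the primary endpoint, and no decision rests on the others.** The first part stands. On the second, the secondaries carry only nominal p-values and no multiplicity procedure (SAP 2.6.1.1, 2.6.2). Their intervals will still be reported against an objective of demonstrating efficacy, so narrower ones have some value.
- **The gain is easily overstated.** This stands. A reader might turn the upper HDL-C figure into an equivalent increase in sample size for the trial. That figure belongs to one secondary analyte with almost no drift, whereas baseline and outcome are about 150 days apart and every participant receives lifestyle instruction.
- **The glucose rule is no precedent.** SAP 5.3 says: "Baseline glucose is defined as the average of the last two non-missing fasting glucose values on or prior to Day 1". A reader might see an inconsistency with the lipid baseline. There is none: it is a derivation rule for a laboratory safety variable, and it averages values, which is not proposed here.
- **The Day 1 sample is inferred.** Fasting at all visits serves lipids and/or glucose, which does not prove a Day 1 lipid draw. The baseline definition and the blinding of lipid results after screening make one likely, but the lipid row of Table 1-2 cannot be read.
- **A late change costs credibility.** If the core part is locked, changing the primary covariates would cost more than a 1–3% smaller SE is worth. This stands and limits the fix.

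**Conclusion.** The point holds as an optional efficiency improvement of low priority. The planned ANCOVA is valid, and adding the screening value is an unbiased adjustment that uses data already collected. Expected fall in the variance of the treatment difference: about 2–6% for LDL-C, with no effect on the primary conclusion; about 5–13% for TG; about 5–20% for HDL-C. The upper ends apply only if there is little true drift to Day 150.

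These sizes rest on assumed between- and within-person variation, response SD and drift, none of which the documents give, and on a Day 1 lipid sample separate from screening. The direction was the same in every scenario; the size is uncertain.

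**What to change.** 1. In SAP 2.5.2 and 2.6.1.1, add the screening value of the same analyte as a second continuous covariate for LDL-C, TC, TG, HDL-C, non-HDL-C, ApoB and ApoA-1. Keep the Day 1 value as the denominator; averaging the two would redefine the endpoint.
2. Add the same term to the imputation models in SAP 5.4.1.1, so that imputation and analysis condition on the same data. SAP 5.4.2 and the supplementary and subgroup analyses refer back to these models, so state whether they inherit the term.
3. Leave PCSK9 and Lp(a) unchanged unless they are measured at screening.
4. State the rule for a missing Day 1 value. Screening then becomes the baseline and no second reading exists; one option is to enter the same value for both covariates.
5. Align Protocol 9.3.2 and 9.4.1.1, or record the departure in SAP section 4, which now lists none.
6. If the core part database is already locked, keep the planned model as primary and add this only as a labelled supportive analysis.

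Cost: one degree of freedom, no new data, and slightly different models across analytes, which departs from the present rule of one common ANCOVA for all core part secondaries.

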### 2.5.3 Handling of intercurrent events

The primary efficacy analysis will account for different intercurrent events as explained in the following:

- **Discontinuation of study treatment:** Retrieved drop out (RDO) data collected after discontinuation from study treatment will be used for the analysis (treatment policy). Missing data after discontinuation from study treatment will be multiply imputed based on RDO data within each treatment group, and when there are no sufficient RDO data, a control-based Pattern-Mixture Model (PMM) will be used for multiple imputation. In the PMM, missing not at random (MNAR) assumption will be used for inclisiran group. The detailed information is specified in [Appendix 5.4.1.1](#).
- **Use of prohibited LLT:** Use of prohibited LLT (PCSK9 monoclonal antibodies taken before Day 150 visit assessment or other LLT taken within 30 days before Day 150 visit assessment) will be treated in a hypothetical scenario of what would happen had those LLT not been taken, and those participants behaved like other participants in the same treatment group (hypothetical strategy). Data after those intercurrent events will be

excluded for the analysis and will be multiply imputed within each treatment group under MAR assumption.

- **Death:** Death due to CV or non-CV causes is considered as an unfavorable outcome (composite strategy). The LDL-C values at Day 150 after death will be set using the participant's baseline values.

In the case of multiple intercurrent events, death will be the dominant one in the analysis (if present). If a participant experiences only two other intercurrent events and usage of prohibited LLT occurs first, s/he will be handled by the event of usage of LLT (hypothetical strategy). If treatment discontinuation occurs prior to usage of prohibited LLT, then data after usage of LLT will be set missing and s/he will be handled by the event of treatment discontinuation (treatment policy). The detailed imputation model and algorithm are specified in [Appendix 5.4.1.1](#). Number and percentage of participants by each intercurrent event will be summarized by treatment group in core part analyses. Listing will also be provided.

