6.8.2 Prohibited medication

Use of the treatments displayed in the below table are not allowed. This table is not considered all-inclusive. If in doubt, the investigator should contact Novartis medical monitor before randomizing a participant or allowing a new medication to be started. If the participant is already enrolled, contact Novartis to determine if the participant should continue his/her participation in the study.

Table 6-4 Prohibited medication

Medication	Prohibition period	Action taken
Any lipid-lowering therapy other than PCSK9 targeted therapies including statins (including Xuezhikang), ezetimibe, bempedoic acid, fibrates, bile-acid sequestrants, niacin and omega-3 fatty acids (DHA and/or EPA with a total dose > 1000mg), or any drug with unknown ingredients taken for the purpose of lipid-lowering, including over-the-counter or herbal therapies.	At least 90 days prior to screening and throughout the study.	Investigators should request participants to stop taking these medications. If participants decide to continue taking them, or need to take them in the judgment of the investigators, it must be recorded in the source documentation and on an appropriated eCRF page.
PCSK9 monoclonal antibodies	At least 90 days prior to screening and throughout the study.	Discontinue study treatment
Any other non-mAb PCSK9-targeted therapy other than study drug (also including commercially available inclisiran).	At least 2 years prior to screening and throughout the study	Discontinue study treatment
Any RNAi-based therapeutics, including but not limited siRNA or Antisense Oligonucleotide (ASO) therapeutics.	At least 2 years prior to screening and throughout the study	Discontinue study treatment
Any other investigational treatment	At least 30 days or 5 half-lives, whichever is longer, prior to screening and throughout the study	Discontinue study treatment

7 Discontinuation of study treatment and participant discontinuation/withdrawal

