### **1.2.1 Primary estimand(s)**

The estimand is the precise description of the treatment effect and reflects strategies to address events occurring during trial conduct which could impact the interpretation of the trial results (e.g. premature discontinuation of treatment).

The clinical question of primary interest is: what is the reduction in LDL-C, quantified by difference of mean percentage change from baseline at Day 150, in Chinese adults with low or moderate ASCVD risk and elevated LDL-C who are not on any lipid-lowering therapy, who receive inclisiran as monotherapy, compared to placebo, regardless of discontinuation from study treatment, if other lipid-lowering therapy were not taken, and where death due to CV or non-CV causes is considered an unfavorable outcome.

The primary estimand is described by the following attributes:

Population: Chinese adults with low or moderate ASCVD risk and elevated LDL-C who are not on any lipid-lowering therapy.

Endpoint: Percentage change from baseline at Day 150 in LDL-C.

Treatments of interest: Inclisiran as monotherapy compared to the use of placebo, regardless of study treatment discontinuation.

Handling of intercurrent events:

- Permanent discontinuation of study treatment will be handled with a treatment policy strategy, keeping treatment labels as assigned at randomization.

- Use of prohibited LLT (PCSK9 monoclonal antibodies taken before Day 150 visit assessment or other LLT taken within 30 days before Day 150 visit assessment) will be treated with a hypothetical strategy of what would happen had those LLT not been taken and those participants behaved like other participants in the same treatment group.
- Participants who died will be handled with a composite strategy; death is considered an unfavorable outcome.

Summary measure: the summary measure to be used is the difference of mean percentage changes.

Complete details on the statistical methods and inference, including missing data handling and sensitivity analyses are provided in [Section 2.5](#).

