### 5.1.3 Concomitant medication date imputation

For LLT, the end date will be imputed using below rules.

Year missing	Set the earliest of (last visit date, date of death, analysis cutoff date)
Month missing	Set the earliest of (last visit date, 31DecYYYY, date of death, analysis cutoff date)
Day missing	Set the earliest of (last visit date, last date of reported month, date of death, analysis cutoff date)

If imputed end date is prior to start date, set the end date using start date.

For other medications, the partially missing concomitant medication start/end date will be imputed using the Novartis ADaM Governance Board (AGB) global standard approach. Details will be provided in the study PDS.

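### The prohibited-LLT event counts earlier use only for PCSK9 antibodies, so a control given commercial inclisiran before about Day 120 keeps a drug-lowered Day 150 LDL-C as placebo data

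*SAP*

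**What the plan says.** The LLT event has two limbs: "PCSK9 monoclonal antibodies taken before Day 150 visit assessment or other LLT taken within 30 days before Day 150 visit assessment" (SAP 2.5.3; the same definition is in SAP 1.2.1 and Protocol 3.1 and 9.3.3). It is handled by a hypothetical strategy, because the clinical question asks for the effect "if other lipid-lowering therapy were not taken" (SAP 1.2.1). Step 1 of SAP Appendix 5.4.1.1 blanks LDL-C values only for participants who had this event.

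Stopping study treatment is handled by treatment policy, so observed values are kept under the randomized label. Where both events occur, SAP 2.5.3 adds: "If treatment discontinuation occurs prior to usage of prohibited LLT, then data after usage of LLT will be set missing".

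Protocol Table 6-4 gives antibodies one row and a further row to "Any other non-mAb PCSK9-targeted therapy other than study drug (also including commercially available inclisiran"). The prohibition period for that row is "At least 2 years prior to screening and throughout the study", against 90 days before screening for antibodies. Use of either requires study treatment to stop. SAP 2.4.2 also lists inclisiran apart from PCSK9 antibodies among the LLTs to be identified, and says of the coding: "Detailed specifications will be provided separately".

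**The concern.** Inclisiran is not an antibody, so under this definition it is at most an other LLT with a 30-day look-back. The agent with the longer exclusion before screening gets the shorter look-back before the endpoint.

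For a control participant, the rule keeps a value measured under the test drug itself and counts it as placebo data. That pulls the estimated difference toward zero. An inclisiran-arm participant who stops study drug and then takes such an agent before the window also keeps the value. That bias runs the other way, and it is smaller while the earlier study dose still acts.

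What is at stake is the match between the primary estimand and its analysis, and slightly the size of the estimate. The superiority conclusion is not at stake.

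**Working it through.** **1. Which doses escape.** The Day 150 visit has a window of ±7 days (Protocol 1.3). The 30-day boundary is the visit day minus 30:
- 143 − 30 = Day 113
- 150 − 30 = Day 120
- 157 − 30 = Day 127

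An on-study dose outside the window is 31 to 149 days old at a nominal Day 150 visit (150 − 1 = 149), or up to 156 days old at a Day 157 visit.

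**2. Is the drug still acting then?** Protocol 4.3 reports LDL-C change 180 days after a single 300 mg dose without other LLT, and supports six-monthly dosing. SAP 2.4.1 adds 180 days after the last dose when it computes exposure. Since 156 < 180, every escaping dose is still inside the duration the documents use.

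**3. Does another rule catch it?**
- Step 1 of Appendix 5.4.1.1 and the ordering rule both need a prohibited-LLT event. There is none.
- If study treatment stops, as Table 6-4 requires, treatment policy keeps the Day 150 value. If it does not stop, the value is ordinary observed data.
- The tipping-point analysis (SAP 2.5.5) varies imputed inclisiran-arm values only.
- Supplementary analysis 2 applies treatment policy to LLT use and keeps the value.
- Supplementary analysis 1 removes the value if the discontinuation is recorded, but it targets a different estimand.

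**4. Size per affected control.** The plan gives about 200 participants, 1:1, with no effect, SD or power, so there is no power figure to reproduce. Protocol 2.2 gives placebo-adjusted reductions of 47.9% (low end of the global phase 3 trials, Day 510) and 57.2% (Asian phase 3 trial, Day 330). Both follow repeated doses. No single-dose percentage is given, so 30% is an assumed lower value.

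With k affected controls out of 100, each carrying effect e, the control-mean shift is e × k / 100:

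| e (%) | k = 1 | k = 3 | k = 10 |
|---|---|---|---|
| 30 | 0.30 | 0.90 | 3.00 |
| 47.9 | 0.48 | 1.44 | 4.79 |
| 57.2 | 0.57 | 1.72 | 5.72 |

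**5. Against the standard error.** SE = SD × √(2/100), which is 2.12 at SD 15 and 5.66 at SD 40 (both SDs assumed). One affected control is between 0.30/5.66 = 0.05 and 0.572/2.12 = 0.27 of a standard error.

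**6. Stress case.** Take k = 10, SD 40 and true effect E. The difference is E − 0.1e. The control variance is 40² + 0.1 × 0.9 × e². Power is Φ(difference/SE − 1.96).
- E = 30, e = 30: difference 27.0, SE 5.73, ratio 4.7, power 99.7%.
- E = 30, e = 57.2: difference 30 − 5.72 = 24.3; SE = √((1894.5 + 1600)/100) = 5.91; ratio 4.1; power 98.4%.
- E = 47.9, e = 57.2: difference 42.2, SE 5.91, ratio 7.1.

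**The case against.** The best counter-argument is that the case is unlikely and the documents cannot fully settle it. Entry requires no plan for other LLT, lipid results are blinded, and local lipid testing is discouraged (Protocol 5.1, 8.3.1). No frequency is given, and the documents do not say that inclisiran was on sale in China during recruitment. This stands, and it is why the point is minor. Table 6-4 nevertheless names commercial inclisiran, so the sponsor foresaw the case.

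Coding and dating of injections sit in specifications outside the SAP. If inclisiran is coded as other LLT, a record with no end year is dated by the rule "Set the earliest of (last visit date, date of death, analysis cutoff date") (SAP 5.1.3), which may bring it into the 30-day window. A second dose inside the window would also be caught. Both points stand. The gap is therefore limited to completed records with no later dose in the window.

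The LLT table in SAP 2.4.2 counts "participants who received the corresponding medication on or prior to the following select time points", including Day 90 and Day 150. A zero for inclisiran by Day 150 would close the commercial-inclisiran case. A nonzero count would only bound the number affected, and other non-antibody PCSK9 agents have no row of their own.

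Finally, the dilution figures are first-order. Retained control values also feed the within-arm imputation and, if the control-based model is used, the imputed inclisiran-arm values, where they act in the opposite direction. This is true but secondary, because it matters only for imputed values.

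**Conclusion.** The concern holds and is minor. The SAP follows the protocol's wording faithfully, so the weakness lies in the event definition and not in a conflict between the two documents. For a use the protocol itself foresees, the primary analysis keeps a value that its clinical question excludes.

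The bias is about 0.3 to 0.6 percentage points per affected control, toward zero. Per affected inclisiran-arm participant it is at most the same size, in the opposite direction. These figures assume 100 per arm, an effect of 30% to 57.2% in the affected participant, and otherwise no change. The number affected is unknown and may be zero. The superiority test withstands ten affected controls under the least favourable values tried.

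The Day 330 rule has the same wording (Protocol 3.2.2, 9.4.1.2; SAP 1.2.2.2, 2.6.3.2). That endpoint is descriptive and covers the inclisiran group only, so the control-arm mechanism does not arise there.

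**What to change.** **If the core database is not locked:** extend the any-time limb to any PCSK9-targeted therapy other than study drug, taken after first dose and before the Day 150 visit assessment. Keep 30 days for the remaining LLTs and leave Table 6-4 as it is. Make the change in Protocol 3.1 and 9.3.3 and SAP 1.2.1 and 2.5.3, and align the Day 330 sections. Add a medication flag for non-antibody PCSK9 agents, since the inclisiran category in SAP 2.4.2 does not cover them all. The text change is one phrase per definition plus the flag, but the protocol edits need a formal amendment with its approvals (Protocol 10.1.8.1). A few more values may be imputed.

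**If core lock has passed:** this is likely, since SAP Amendment 1 is marked as before core lock and Amendment 2 as before final lock. Leave the primary analysis unchanged. Count affected participants per arm from medication dates relative to each actual Day 150 visit. If the count is zero, nothing more is needed. If not, add a sensitivity analysis under the extended definition, labelled post hoc and recorded in SAP section 4. The cost is one count per arm and, at most, one extra run.
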